Control Intervention (if applicable):	Not applicable			
Number of Participants with Rationale:	Participants of the ongoing population based GAPP cohort study conducted in Liechtenstein will be included (n=2170; study approved by KEK ZH StvNr. 66/09). These will receive the AVA bracelet for free. We eventually might attain a sample size of 5000 participant by onboarding additional participants. For this second phase, we will seek separate ethical approval.			
Study Duration:	The course of the pandemic can currently not be predicted and is critical for the duration of the study. WE anticipate a duration of nearly 3 years.			
Study Schedule:	Participants should be included as fast as possible, in order to catch as many endpoints during the COVID-19 pandemic.			
	Planned 12/04/2020 of First-Participant-In			
	Planned 31/12/2021 of Last-Participant-Out			
	Depending on the course of the pandemic, the study can be terminated earlier.			
Investigator(s):	[name].med. [name], McMaster University, Hamilton ([contact]), Dr.med. [name], Private University Liechtenstein, Triesen ([contact]), [name], Universität Basel ([contact]), [name] MSc, Private University Liechtenstein ([contact]), Dr.[name] PhD, Chief medical Officer AVA for women ([contact])			
Study Centre(s):	Single-centre study. GAPP-Studie c/o labormedizinisches zentrum [name], [name]			
Statistical Considerations:	Prediction of the development of COVID-19 infection will be modeled on the base of nightly monitoring of temperature, breath rate, pulse rate and movements by means of machine learning methods. Algorithms will be trained by comparing monitoring data of COVID-19 diseased and non-diseased individuals by a big data approach employing machine learning. The project partner AVA for women has already used such an approach to predict fertile days in women with a higher than 90% accuracy. The seroprevalence of COVID-19 will be presented as count (percentage) and we			
	will standardize these numbers to the general population of the Principality of Liechtenstein. The sample size is given by the sample size included in the GAPP study.			
GCP Statement:	This study will be conducted in compliance with the protocol, the current version of the Declaration of Helsinki, ISO EN 14155 as well as all national legal and regulatory requirements.			

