3 STUDY OBJECTIVES AND DESIGN

3.1 Hypothesis and primary objective

We hypothesize that by monitoring temperature, breath rate, pulse rate, and movements, it is possible to predict the occurrence of COVID-19 infection. We hypothesize, that temperature will increase due to inflammation/infection, breath rate will increase due to subclinical affection of lungs by COVID-19, heart rate variability as an indicator of stress will be diminished both as a consequence of infection also reflecting severity of infection. Further, we anticipate that registration of characteristic movements also allows to recognize cough. Fever, breathing problems, and cough are all clinical cornerstones in the diagnosis of COVID-19 infection. WE further hypothesize that the alterations in measured parameters antecede the occurrence of clinical symptoms.

Primary objective

A.) To see whether the AVA bracelet is capable to reliably identify persons with COVID19 infection early, before they get clinically. This would allow for early isolation and testing of contact persons, thereby preventing extensive spreading of the Virus. When reversing the process of lockdown of social and economic systems or during a so called second wave of the COVID-19 pandemic, the AVA bracelet could serve as a sensitive tool to observe relapsing infection rates.

Secondary objective

- a.) To see whether the AVA bracelet would serve to recognize severe cases early allowing for risk stratification, early treatment and allocation of adequate care to patients with COVID19.
- b.) To obtain a seroprevalence of COVID19 affected cases in the population of Liechtenstein.

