4 STUDY POPULATION AND STUDY PROCEDURES

4.1 Inclusion and exclusion criteria, justification of study population

The GAPP study is a population based national cohort including 2170 study participants aged 25 to 41 at baseline. This number relates to about 32% of the whole population. Since the study was started to enrol participants from 2010, the study participants are now 35 to 51 years old ⁸.

The GAPP study (study homepage www.blutdruck.li) is an ongoing national cohort study done in the principality of Liechtenstein with a cooperation from the University Basel, Private University Liechtenstein, McMaster University Hamilton, and the labormedizinische zentrum [name] in Liechtenstein. Between 2010 and 2014 all inhabitants of Liechtenstein aged 25-41 years old were asked to participate in the study, and 2170 could be enrolled. The aim of the study is to identify the determinants for the development of hypertension and other cardiovascular risk factors. A large number of baseline characteristics and health information was collected in all participants. Several blood, urinary and genetic markers were collected. By ongoing follow-up we collect information on changes in health information and other characteristics are collected. Currently the second follow-up cycle is ongoing.

GAPP is very well established scientifically. More than 30 scientific manuscripts have been published so far, some of them in major international journals ⁸⁻⁴¹. Therefore, the quality of the data collection is well recognized. In summary, the GAPP study provides a unique platform that would allow rapid evaluation of a promising medical device that has the potential to alleviate the suffering through the current COVID-19 pandemic.

The choice of the study population is ideal, as the organization is already in place, the study participants are already enrolled. With such a setting, the important and urgent study question can be addressed immediately.

Inclusion criteria:

- Participant of the GAPP study
- Providing consent to the present study

Exclusion criteria:

- Inability to provide informed consent

It is not planned to include vulnerable participants into the study.

After a first phase of including participants from the GAPP-study, we eventually might attain a sample size of 5000 participant by onboarding additional participants. For this second phase, we will seek separate ethical approval.

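### Seroprevalence for all of Liechtenstein is not estimable from a cohort aged about 31 to 51 without assuming the same seroprevalence at all other ages

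*Protocol*

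**What the plan says.** Secondary objective b (section 3.1, repeated in the synopsis) is "To obtain a seroprevalence of COVID19 affected cases in the population of Liechtenstein". No age limit is attached.

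The analysis is fixed in one sentence of the synopsis, under Statistical Considerations: "The seroprevalence of COVID-19 will be presented as count (percentage) and we" "will standardize these numbers to the general population of the Principality of Liechtenstein". Section 5.1 does not return to seroprevalence, and section 3.2 does not list it among the endpoints.

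Eligibility in the synopsis and section 4.1 is limited to participants of the GAPP cohort. On its origin, section 4.1 says: "Between 2010 and 2014 all inhabitants of Liechtenstein aged 25-41 years old were asked to participate in the study, and 2170 could be enrolled". On current age it says: "Since the study was started to enrol participants from 2010, the study participants are now 35 to 51 years old". On coverage it says of the 2170: "This number relates to about 32% of the whole population".

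A later enlargement to 5000 with people from outside the cohort is mentioned as a possibility. It would need separate ethical approval and an amendment, and no ages are given for it.

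**The concern.** The stated target is everyone living in the country; the sample is a band of roughly twenty years of age. Children, younger adults and everyone older than the band carry weight in the general population but contribute no observations. The choice of standardising variables, which a statistical analysis plan could settle, does not change that. The mismatch lies in what the protocol itself fixes: the target population and the eligibility rule.

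At stake is one of the two secondary objectives. A figure labelled as standardised to the general population would be read as a national seroprevalence, while the part of it that concerns the unsampled ages would rest on an assumption the reader is never shown.

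**Working it through.** **1. Age range of the cohort.** Inputs from section 4.1: enrolment age 25 to 41, enrolment 2010 to 2014.

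- The protocol's 35 to 51 is reproduced only if everyone enrolled in 2010: 25 + 10 = 35 and 41 + 10 = 51.
- With the stated enrolment period, the youngest in 2020 is 25 + (2020 - 2014) = 31 and the oldest is 41 + (2020 - 2010) = 51.

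The range at baseline is therefore about 31 to 51, and the stated lower limit is up to 4 years too high. The synopsis plans serology at the beginning and the end of the study, with the last participant out on 31/12/2021. By then the range is about 25 + 7 = 32 to 41 + 11 = 52, and someone who was 41 in mid-2010 may already be 53.

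**2. The 32%.** Read literally, 2170 / 0.32 = 6,781 residents of all ages. Only people aged 25 to 41 were invited, so the 32% fits that age group better than the country. The protocol gives no national total with which to confirm this.

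**3. What the standardised figure estimates.** Let p_in be the seroprevalence inside the sampled ages, w the share of residents in those ages, and r the ratio of seroprevalence outside to inside. Then

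- national seroprevalence = p_in × [w + (1 - w) × r];
- a figure built only on the sampled ages, however weighted by age and sex within them, estimates p_in;
- relative error of that figure as a national value = 1 / [w + (1 - w) × r] - 1.

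The protocol gives neither w nor r. With w assumed at 0.2 to 0.4 and r at 0.5 to 1.5:

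| r | w = 0.2 | w = 0.3 | w = 0.4 |
|---|---|---|---|
| 0.5 | +66.7% | +53.8% | +42.9% |
| 0.75 | +25.0% | +21.2% | +17.6% |
| 1 | 0% | 0% | 0% |
| 1.25 | -16.7% | -14.9% | -13.0% |
| 1.5 | -28.6% | -25.9% | -23.1% |

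For example, w = 0.2 and r = 0.5 give 0.2 + 0.8 × 0.5 = 0.6, and 1 / 0.6 - 1 = +66.7%.

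**4. Scale against sampling error.** Assume 5% inside the band and blood from all 2170. The 95% half-width is 1.96 × √(0.05 × 0.95 / 2170) = 0.92 percentage points. At w = 0.2 the national value would be 5% × 0.6 = 3.0% for r = 0.5, or 5% × 1.4 = 7.0% for r = 1.5. Either is 2 points from the reported 5%, a gap that a confidence interval would not reflect.

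**The case against.** The best defence is that seroprevalence is a secondary aim, the promise to standardise is one clause of the synopsis, and the method would normally be set out in a statistical analysis plan that is not shown here. All of that is true, and it limits the weight of the point. It does not remove it, because no later detail can provide data for ages that the eligibility rule excludes.

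Several stronger readings are tempting, and the document does not support them:

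- *That the national figure will be wrong.* If seroprevalence outside the sampled ages equals that inside, the error is zero. Neither the size nor the sign of any error can be derived from the protocol.
- *That only a crude percentage will be reported.* The sentence promises a count and percentage and also standardisation. Giving both is normal practice.
- *That there will be no confidence interval and that false positives will be counted as infections.* The protocol is silent on both. Intervals and correction for assay sensitivity and specificity are commonly left to the analysis plan. They are advisable here, but their absence is not an error of this protocol.
- *That the 35 to 51 and the 32% corrupt the standardisation.* They are descriptive statements. The weights would come from resident counts and the participants' actual ages.

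**Conclusion.** The point holds in this form: the protocol commits to a seroprevalence for the general population that its sample, aged about 31 to 51 in 2020, cannot identify without an unstated assumption of equal seroprevalence at the unsampled ages. The lack of data at those ages follows from the protocol's text alone. The size does not: the range of about +67% to -29% is an illustration under the assumed share of 20-40% and ratio of 0.5 to 1.5, and it includes zero.

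Two smaller faults in section 4.1 go with it. The current age range contradicts the enrolment period given in the same section, and the 32% is attached to a denominator that does not fit the group invited. The primary objective is not affected.

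**What to change.** - Restrict secondary objective b (section 3.1 and synopsis) and the standardisation sentence of the synopsis to residents in the age range the cohort covers at each blood draw: about 31 to 51 at baseline in 2020, and about one to two years older at the end of the study. One fixed band of 31 to 51 for both draws would leave out the oldest participants at the end.
- Standardise by sex and age group within that range. This removes the age-coverage error by construction; it does not address who chose to take part.
- If a national figure is still wanted, sample the other ages under the amendment already foreseen, or state the equal-seroprevalence assumption openly and show how the figure moves when it is varied.
- In section 4.1, reconcile the stated 35 to 51 with enrolment in 2010 to 2014 (about 31 to 51), and give the true denominator of the 32%. It is apparently the invited age group; the sponsor should confirm.

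Restricting the target needs only changes of wording and a routine calculation, with no new data. The price is a narrower claim. A confidence interval and a correction for assay error would be sensible additions if the analysis plan does not already contain them.

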2 BACKGROUND AND RATIONALE

The WHO has declared the current coronavirus (COVID-19) outbreak to be a pandemic and therefore a Public Health Emergency of International Concern. It is crucial to rapidly gain a better understanding of the newly identified virus, especially in relation to potential clinical and public health measures that can be immediately used to improve patients' health and/or contain the spread of COVID-19. In particular, development of early and reliable detection of COVID-19 carriers and symptomatic individuals suspected of COVID-19 infection is needed. We are proposing to test the utility of a CE marked, marketed medical device that can continually track changes in physiological parameters in detecting early signs of a COVID-19 infection. In particular, the device's ability to register increases in physiological parameters associated with fever (e.g., resting pulse rate, breathing rate, and skin temperature) could render it an ideal candidate during screening point of care (POC), both for potential COVID-19 infections in asymptomatic, exposed users and asymptomatic users unsure of their exposure status.

This proposal aims to optimize efficient patient management, public health preparedness, and response to current and future outbreaks of COVID-19 infection; leveraging an existing medicalgrade technology may allow clinicians and researchers to more rapidly evaluate patients' wellbeing, thereby enabling faster case detection. Additionally, healthcare professionals and researchers may benefit from using this device to monitor patients with confirmed cases of COVID-19. Synced to a central app via Bluetooth, the device measures physiological parameters continuously while the user sleeps; its design inherently alleviates the need for healthcare professionals to take the patient's temperature, breathing rate and pulse rate. We believe that, by reducing the in-person contact between patients and their care team, the AVA bracelet could also lower potential transmission rates among nurses, doctors, and/or researchers studying COVID-19's development ¹. This medical device is able to measure skin temperature, pulse rate, and breathing rate simultaneously, and thus may prove helpful in combatting a public health crisis through its potential to rapidly detect novel COVID-19 cases and enable remote surveillance of .

Studies on COVID-19, including one conducted by the World Health Organization's Joint Mission with China, reported that fever (87.9% of cases), dry cough (67.7% of cases), and shortness of breath (18.6% of cases) are the most frequent presenting symptoms ²⁻⁴. Close to half (44%) of infected Chinese patients reported to treatment centers with fever as their first presenting symptom ². Our proposal is to test the utility of a CE-marked, marketed, wrist-worn medical device (AVA bracelet) that tracks breathing rate, pulse rate, skin temperature, heart rate variability and skin perfusion to generate data on potential early signs of COVID-19 in users at home ¹. While not specific to COVID-19, during a fever, body temperature and pulse rate increase ⁵⁻⁷ and shortness of breath can be measured by increased breathing rate. In a person with a known COVID-19 exposure, these signs could be indicative of an infection and helping with triaging for medical care ⁵. A recent paper examining the validity of wrist temperatures compared to forehead and tympanic temperatures among Chinese COVID-19 patients found less overall variability in wrist temperatures ⁵.

The authors assessed individuals' temperatures upon their arrival to the medical clinic, demonstrating the importance of reliable knowledge about patients' vital signs at time of triage. Our research vision takes this finding a step further; what if, for example, healthcare professionals and doctors had patient-provided access to a record of their pulse rate, temperature, and breathing rate over the past week or month, measured by a regulatory-approved medical device? Could this help expedite triaging and lead to more data-informed decisions around identifying potential cases for reference to a medical setting where they could receive official diagnosis and treatment? Alternatively, a study could also probe the utility of the AVA bracelet as a remote continuous measurement device, worn during sleep to monitor for potential infection in exposed or high-risk populations in self-isolation at home. These are just some of the initial research questions we have identified as potential applications for the AVA bracelet; collaborative scientific inquiry and further proposals are welcome, as we consider how to best enlist our medical device in the management of COVID-19.

The AVA bracelet automatically saves physiological information every 10 seconds throughout the

night, requiring at least 4 hours of relatively uninterrupted sleep each night to stabilize parameter measurements ¹. The wrist-worn bracelet acts as a data logger, recording and storing user's physiological sensors signals as raw datasets throughout the night. Currently, the user synchronizes the bracelet to the mobile application the following morning. The mobile app reads the raw datasets via Bluetooth Low Energy (BLE) and transfers them to the backend. After computation and preprocessing of the physiological parameters based on the bracelet's recordings, an algorithm obtains pre-processed physiological parameters changes that are transferred back to the mobile app and displayed to the user.

Rapid action is required current the ongoing pandemic. The GAPP study is ideally suited to function as a platform to test the AVA device in a population with a high exposure to COVID-19 viruses and a high prevalence of testing ⁸. GAPP is ongoing and therefore this project can be launched in a very short time period.

The intervention of observing study participants with the AVA bracelet, a medical device, together with planned blood drawings entails only minimal risks and burdens and, according to ClinO Art 20. can be categorized as category A.

3 STUDY OBJECTIVES AND DESIGN

3.1 Hypothesis and primary objective

We hypothesize that by monitoring temperature, breath rate, pulse rate, and movements, it is possible to predict the occurrence of COVID-19 infection. We hypothesize, that temperature will increase due to inflammation/infection, breath rate will increase due to subclinical affection of lungs by COVID-19, heart rate variability as an indicator of stress will be diminished both as a consequence of infection also reflecting severity of infection. Further, we anticipate that registration of characteristic movements also allows to recognize cough. Fever, breathing problems, and cough are all clinical cornerstones in the diagnosis of COVID-19 infection. WE further hypothesize that the alterations in measured parameters antecede the occurrence of clinical symptoms.

Primary objective

A.) To see whether the AVA bracelet is capable to reliably identify persons with COVID19 infection early, before they get clinically. This would allow for early isolation and testing of contact persons, thereby preventing extensive spreading of the Virus. When reversing the process of lockdown of social and economic systems or during a so called second wave of the COVID-19 pandemic, the AVA bracelet could serve as a sensitive tool to observe relapsing infection rates.

Secondary objective

- a.) To see whether the AVA bracelet would serve to recognize severe cases early allowing for risk stratification, early treatment and allocation of adequate care to patients with COVID19.
- b.) To obtain a seroprevalence of COVID19 affected cases in the population of Liechtenstein.

3.2 Primary and secondary endpoints

Primary endpoint is the occurrence of COVID-19 infection, as assessed by clinical signs, serology and/or RT-PCR testing Date of occurrence, clinical symptoms and laboratory results, how infection was diagnosed is collected to describe the primary endpoint. The endpoints will be collected by periodic reports obtained on questioning the study participants. Participants and the

treating healthcare institutions will be contacted to obtain respective information.

As a secondary endpoint severity of COVID-19 infection will be assessed. Participants and the treating healthcare institutions will be contacted to obtain respective information. The following parameters will be collected: Hospitalization needed within 30 days of COVID-19 diagnosis (including timing)? ICU admission within 30 days of COVID-19 diagnosis (including timing)? Use of mechanical ventilation within 30 days of COVID-19 diagnosis (including timing)? Participant reported health status after COVID-19 diagnosis (including timing)? COVID-19 related mortality? Quantiative RT-PCR results (viral loads) and quantitative Immunoassay results of COVID-19 specific laboratory markers? Results of other respiratory pathogens in COVID-19 negative participants available? Further healthcare contact of patients tested negative for COVID-19?

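### The primary endpoint lets clinical signs alone make a COVID-19 case, so the training label is not independent of the physiology the bracelet measures

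*Protocol*

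**What the plan says.** Protocol section 3.2 defines the endpoint: "Primary endpoint is the occurrence of COVID-19 infection, as assessed by clinical signs, serology and/or RT-PCR testing". It does not rank the three kinds of evidence and does not make a laboratory result a condition. The method of diagnosis is recorded, but only as description: "how infection was diagnosed is collected to describe the primary endpoint". On the source of the data it says: "The endpoints will be collected by periodic reports obtained on questioning the study participants". Treating institutions are contacted as well.

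Section 3.1 gives the hypothesis: "by monitoring temperature, breath rate, pulse rate, and movements, it is possible to predict the occurrence of COVID-19 infection". On the movement channel it adds: "we anticipate that registration of characteristic movements also allows to recognize cough". On diagnosis it says: "Fever, breathing problems, and cough are all clinical cornerstones in the diagnosis of COVID-19 infection". Section 2 concedes the limit of these signals: "While not specific to COVID-19, during a fever, body temperature and pulse rate increase". The synopsis, under statistical considerations, says what the label is for: "Algorithms will be trained by comparing monitoring data of COVID-19 diseased and non-diseased individuals".

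Three other provisions bear on the point. Sections 3.4 and 4.3 send symptomatic participants for testing under national guidelines, and section 4.3 places this in routine care. Blood is taken for serology at study end. Sections 2 and 4.3 describe processed parameter changes being shown to the wearer in the app.

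**The concern.** An algorithm meant to recognise COVID-19 has to be trained and judged against a label that does not depend on the signals it reads. Here the signs that may make someone a case are, by the protocol's own account, the clinical counterparts of the temperature, breath-rate and movement channels. Influenza or any other febrile respiratory illness could produce both the signal and, if called COVID-19 on signs, the label.

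A detector that recognises fever of any cause would then be credited with finding COVID-19. False alarms in people with another illness would be counted as correct detections. The primary objective, reliable early identification of persons with COVID-19, could not be told apart from detection of febrile illness in general.

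**Working it through.** **Text check.** The steps are:

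1. The list in section 3.2 is joined by and/or. Read normally, any one element suffices, including clinical signs.
2. The method of diagnosis describes the endpoint and does not restrict it.
3. Testing of symptomatic participants (3.4, 4.3) and end-of-study serology are study procedures. Neither is tied to the endpoint, and no sentence says how a signs-based case with negative or missing tests is classified.
4. Section 3.1 links fever to temperature, breathing problems to breath rate, and cough to movement. The last is an expectation only. Pulse rate and heart rate variability are measured but are not among the three named diagnostic signs.
5. The synopsis uses diseased versus non-diseased status as the training target.

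**Illustrative size.** The protocol has no figure to reproduce: 2170 is the size of the existing cohort, not a calculated sample size. Everything below except 2170 is an assumption.

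- COVID-19 attack rate: 5% (range 1–10%).
- Other febrile or respiratory illness: 20% of participants (range 10–30%).
- Share q of that other illness labelled COVID-19 on signs alone: 0–50%.
- A detector that fires in 80% of any such illness and in 5% of well participants, and cannot tell COVID-19 from other illness.

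Middle scenario:

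- True cases = 2170 × 0.05 = 108.5.
- Other illness = 2170 × 0.20 = 434.
- Well = 2170 − 108.5 − 434 = 1627.5.
- Alarms = 0.8 × 108.5 + 0.8 × 434 + 0.05 × 1627.5 = 86.8 + 347.2 + 81.4 = 515.4.
- PPV for true COVID-19 = 86.8 / 515.4 = 0.17.

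With q = 25%:

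- False labels = 0.25 × 434 = 108.5, so the false share = 108.5 / 217 = 0.50.
- Apparent PPV = 0.8 × 217 / 515.4 = 0.34.
- Apparent specificity = 1 − (0.8 × 325.5 + 81.4) / (325.5 + 1627.5) = 0.825. With q = 0 it is 1 − (347.2 + 81.4) / (434 + 1627.5) = 0.792.
- Apparent sensitivity = 0.8 × 217 / 217 = 0.80, unchanged.

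| q | False labels | Share false | Apparent PPV | Apparent specificity |
|---|---|---|---|---|
| 0 | 0 | 0 | 0.17 | 0.792 |
| 10% | 43 | 0.29 | 0.24 | 0.805 |
| 25% | 108.5 | 0.50 | 0.34 | 0.825 |
| 50% | 217 | 0.67 | 0.51 | 0.862 |

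Over the whole assumed grid with q from 10% to 50%, the false share runs from 9% to 94%:

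- Lowest (10% COVID-19, 10% other illness, q = 10%): 21.7 / 238.7; PPV goes from 0.40 to 0.44.
- Highest (1% COVID-19, 30% other illness, q = 50%): 325.5 / 347.2; PPV goes from 0.03 to 0.45.

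**The case against.** The strongest reply is that the wording can also be read as clinical signs together with serology and/or RT-PCR. The surrounding text leans towards laboratory work-up: symptomatic participants are sent for testing, section 2 cites a high prevalence of testing, and section 3.2 itself speaks of participants who tested negative. This shows that signs-only cases may be few. It does not rescue the definition, because the requirement is not stated. If signs were required, symptom-free infections would be excluded, although section 2 names asymptomatic users as a target.

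A second reply is that laboratory results and method of diagnosis are collected, so a confirmed-case analysis can be run anyway, and that analysis sets belong in an analysis plan that is not at hand. That holds for analysis detail. The endpoint definition, however, is fixed in section 3.2.

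A reader might also infer four stronger things that the documents do not support:

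- That the algorithm is scored against its own inputs. No provision lets bracelet output enter the endpoint; labels come from participants and treating institutions. The dependence is through shared physiology, with the app display as a possible second route.
- That sensitivity is inflated by construction. In the calculation above it stays at 0.80; PPV and specificity move.
- That a case diagnosed on signs cannot test early detection. A dated symptom onset allows the preceding nights to be examined. What a signs-only case cannot show is that the illness that followed was COVID-19.
- That false cases must swamp true ones, because the incidence in section 4.2 gives only 2170 × 1582 / 1,000,000 = 3.4 cases. That is an early-epidemic count, with the accompanying testing figure dated 29 March 2020. It cannot be set against illness accumulating from 12 April 2020 to 31 December 2021, about 20 months.

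**Conclusion.** The point stands as a defect in the endpoint definition. As written, section 3.2 admits cases on non-specific signs that the protocol itself links to the bracelet's signals, and the algorithm is trained on that label. The consequence is apparent PPV and specificity for COVID-19 that are too favourable for a detector of general febrile illness.

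The direction follows from the design; the amount does not. In the middle scenario half the labels are false and apparent PPV doubles, but the attack rate, the rate of other illness, the share labelled on signs and the detector's behaviour are all assumed. Planned testing and serology would push that share down, by an amount the protocol gives no means of estimating.

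**What to change.** In section 3.2, define the primary endpoint as laboratory-confirmed infection: a positive RT-PCR, or seroconversion from a negative baseline sample to a positive later one. The synopsis provides baseline serology and Appendix 1 shows sampling at bracelet distribution, but sections 3.4 and 4.3 mention routine blood only at study end. Align those two sections so that the baseline sample is included.

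Classify illness diagnosed on signs without laboratory confirmation as suspected. Keep it out of both cases and controls in the primary analysis and use it in a sensitivity analysis only. Keep symptomatic participants who tested negative, and were not diagnosed with COVID-19 on signs, as controls. Report specificity in them separately, since they show whether the algorithm separates COVID-19 from other illness. Section 3.2 already plans follow-up data on participants who test negative.

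Restrict the lead-time analysis to laboratory-confirmed cases with a dated symptom onset or a dated positive RT-PCR. Seroconversion alone gives no infection date, because the two samples may lie up to about 20 months apart.

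The cost is a paragraph in section 3.2 and aligned wording in 3.4 and 4.3, using data already planned provided the baseline sample is taken. The price is fewer counted endpoints, and symptom-free seroconverters cannot be aligned to nightly recordings.
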